11.1 Event Classification

Adverse Event (AE):

An adverse event is any untoward medical occurrence, unintended disease or injury, or

untoward clinical signs (including abnormal laboratory findings) in subjects whether or not related to the investigational medical device. This definition includes events related to the AccuFill implant or Subchondroplasty Surgical Instrumentation as well as those related to the Subchondroplasty Procedure.

Serious Adverse Event (SAE):

A Serious Adverse Event is any adverse event that:

- a. led to death.
- b. led to serious deterioration in the health of the subject, that either resulted in:
 1. a life-threatening illness or injury, or
 2. a permanent impairment of a body structure or a body function, or
 3. in-patient or prolonged hospitalization, or
 4. medical or surgical intervention to prevent life-threatening illness or injury or permanent impairment to a body structure or a body function.
- c. led to fetal distress, fetal death or a congenital abnormality or birth defect.

Planned hospitalization for a pre-existing condition, *with the exception of a lower extremity surgical procedure*, or a procedure required by the protocol, without serious deterioration in health, is not considered a serious adverse event.

Adverse Device Effect (ADE):

An Adverse Device Effect is an adverse event related to the use of the AccuFill implant or SCP Surgical Instrumentation (AccuPort Delivery Cannulas). This definition includes adverse events resulting from insufficient or inadequate instructions for use, deployment implantation, installation, or operation, or any malfunction of the medical device, as well as any event resulting from use error or from intentional misuse of the medical device.

For the purposes of this study protocol, all AEs will be assessed for relationship to the AccuFill implant or SCP Surgical Instrumentation. Any AEs considered to be possibly, probably, or definitely related to the implant or SCP Surgical Instrumentation will be considered as potential ADEs in study analysis and/or reporting.

Serious Adverse Device Effect (SADE):

A Serious Adverse Device Effect is an adverse device effect that has resulted in any of the consequences characteristic of a serious adverse event.

Unanticipated Serious Adverse Device Effect (USADE)

An Unanticipated Serious Adverse Device Effect is a serious adverse device effect that is not identified in nature, severity, or degree of incidence in Appendix A. Package Insert.

Device Deficiency

A Device Deficiency is defined as an inadequacy of a medical device with respect to its

identity, quality, durability, reliability, safety or performance. This includes malfunctions, use errors, and inadequate labeling.

11.2 Adverse Event Data Collection

The Adverse Event Form will collect the following:

- Description of Complication (Diagnosis)
- Date of Onset
- Status of Adverse Event or Date of Resolution
- Severity/Intensity of Symptoms
 - Mild: Event/symptom is transient and well tolerated by the subject.
 - Moderate: Event/symptom causes discomfort and interferes with routine activities of the subject.
 - Severe: Event/symptom interferes considerably with the routine activities of the subject or causes inability to work.
- Relationship to Study Surgical Procedure (Subchondroplasty and/or Arthroscopy)
 - Not Related: The adverse event is clearly NOT related to the surgical procedure: the AE follows no known or suspected pattern of response, and an alternative cause is present.
 - Possibly Related: The adverse event may be related to the surgical procedure. The AE follows a suspected pattern of response, or is otherwise logically related to the surgical procedure; however, an alternative cause is present.
 - Probably Related: The adverse event is likely related to the surgical procedure. The AE follows a known or suspected pattern of response or is otherwise logically related to the surgical procedure, but an alternative cause may be present.
 - Definitely Related: The adverse event is directly related to the surgical procedure such that is no alternative cause.
- Relationship to Implant (AccuFill) or Instrumentation (AccuPort Cannulas)
 - Not Related: The adverse event has no temporal or other relationship to the administration of the implant: follows no known or suspected pattern of response and an alternative cause is present.
 - Possibly Related: The adverse event may be related to the implant. The AE has a temporal relationship to the administration of the implant, follows a suspected pattern of response, or is otherwise logically related to the implant; however, an alternative cause is present.
 - Probably Related: The adverse event is likely related to the implant. The AE follows a known or suspected pattern of response or is otherwise logically related to the implant, but an alternative cause may be present.
 - Definitely Related: The adverse event is clearly related to the implant: the adverse event has a temporal relationship to the

administration of the implant, follows a known pattern of response, or is otherwise logically related to the implant and no alternative cause is present

- Treatment
- AE Outcome

The outcome is in relationship to the Adverse Event, not the treatment rendered for the event (if any).

- Recovered: The adverse event has been resolved and/or no further treatment is required to treat the reported condition or illness.
- Recovered with Sequelae: The adverse event has been resolved, however they have retained pathological conditions resulting from the prior disease or injury.
- Not Recovered, Ongoing: Treatment or diagnostic studies were prescribed for the adverse event and the outcome of the adverse event is not yet known.
- Lost-to-Follow-up: The outcome of the adverse event cannot be assessed as the subject has been lost-to-follow-up.
- Chronic, Clinically Stable: The adverse event will most likely never be resolved. The subject “tolerates” the illness or condition as a matter of life.
- Death: The outcome indicates the subject died as a direct result of the reported adverse event.

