11.3 Events Followed to Resolution

Any adverse event considered by the Investigator to be possibly, probably or definitely related to the Subchondroplasty procedure and/or AccuFill should be followed over the study period until resolution or until the Investigator determines the event is chronic or clinically stable.

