14.6 Analysis of Secondary Endpoints

The following secondary endpoints will be examined:

- 1) Comparison of mean change in KOOS Pain, ADL, Symptoms, Sports and Recreation, Quality of Life Subscale scores
- 2) Longitudinal comparison of KOOS subscales over 12 to 24 months post-surgery
- 3) Comparison of mean Numeric Pain, EQ-5D and Global Satisfaction scores, where available
- 4) X-ray evaluation of joint space narrowing, osteophyte and cyst formation and subchondral sclerosis, where available
- 5) MRI analysis of bone marrow lesion variables, where available
- 6) Incidence and time to resolution of post-operative complications and adverse events
- 7) Incidence and time to joint injections, where available
- 8) Incidence and time to re-operations and revisions
- 9) Number of visits to healthcare providers, diagnostic or treatment procedures, and support devices; use of pain medication; and days of productivity lost, where available.

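### The adverse-event outcome code 'Recovered' takes in events that persist but need no treatment, and untreated ongoing events have no correct code, which puts time to resolution at risk

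*Combined protocol and SAP*

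**What the plan says.** Section 11.2 lists what the Adverse Event Form collects. Early in the list is "Status of Adverse Event or Date of Resolution". Treatment and AE Outcome come later as separate items.

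The outcome codes open with a general rule: "The outcome is in relationship to the Adverse Event, not the treatment rendered for the event (if any" (the sentence closes there). Four of the definitions under that rule matter here:

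- The most favourable code reads "Recovered: The adverse event has been resolved and/or no further treatment is required to treat the reported condition or illness". Resolution is thus only one of two routes to it.
- The code for events still open reads "Not Recovered, Ongoing: Treatment or diagnostic studies were prescribed for the adverse event and the outcome of the adverse event is not yet known". A prescription is part of its test.
- The code for resolution with a lasting effect reads "Recovered with Sequelae: The adverse event has been resolved, however they have retained pathological conditions resulting from the prior disease or injury". Here resolution is mandatory.
- The code for lasting events begins "Chronic, Clinically Stable: The adverse event will most likely never be resolved". It leaves out events that are expected to clear.

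The two remaining codes are for loss to follow-up and death.

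Section 11.3 says that events related to the procedure or the implant "should be followed over the study period until resolution or until the Investigator determines the event is chronic or clinically stable". Section 11.4 sets a similar rule for serious events. Sections 6.3 and 14.6 list, as the sixth secondary endpoint, "Incidence and time to resolution of post-operative complications and adverse events". Section 14.7 adds event listings that show resolution status.

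**The concern.** The lead-in tells the site to judge the event and set treatment aside. Two of the definitions under it then turn on treatment. 'Recovered' can be reached because no more treatment is needed, and 'Not Recovered, Ongoing' can be reached only if treatment or tests were prescribed.

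Sections 5.7.2 and 5.7.3 name risks such as loss of skin sensation, muscle weakness, tenderness and swelling. It is reasonable to expect, though the documents do not say so, that some of these will be watched and not treated while they last. Coding them by the letter of 11.2 would show them as recovered.

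The time-to-resolution endpoint and the summary of the safety profile are at stake. Section 6.1 makes incidence and time to resolution part of a stated secondary objective, and Section 7.0 gives monitoring of adverse events as one reason for continuing follow-up after enrolment stopped. All scheduled follow-up is now by telephone (9.7), so no scheduled examination would expose a miscoded event.

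**Working it through.** The plan states no figure on this point, so the check sets the definitions side by side.

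**Step 1. Test case.** Take an event that is still present, has had no treatment or tests prescribed, is expected to clear in time, and occurs in a subject still in follow-up.

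| Outcome code (11.2) | What the definition demands | Does the event fit? |
|---|---|---|
| Recovered | Resolution, or no more treatment needed | Yes, by the second alternative |
| Recovered with Sequelae | Resolution, with a lasting condition | No: not resolved |
| Not Recovered, Ongoing | Treatment or tests prescribed, outcome unknown | No: nothing prescribed |
| Chronic, Clinically Stable | Unlikely ever to resolve | No: expected to clear |
| Lost-to-Follow-up | Subject lost | No |
| Death | Died of the event | No |

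The only literal match is the most favourable code, and it breaks the lead-in rule. 'Recovered with Sequelae' demands resolution while plain 'Recovered' does not, so the weaker test sits on the better outcome.

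**Step 2. Overlaps.** An event unlikely ever to resolve and needing no treatment fits both 'Chronic, Clinically Stable' and 'Recovered'. An event that was treated, needs no more treatment and still persists with its outcome unknown fits both 'Not Recovered, Ongoing' and 'Recovered'. No rule says which code takes precedence.

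**Step 3. Link to the endpoint.** Time to resolution needs a resolution date. Section 11.2 provides a field for it, separate from the outcome code. The plan does not define resolution, does not say how the date field and the outcome code must agree, and gives no censoring rule for events that have not resolved. A form coded 'Recovered' with an ongoing status, or with no date, is possible under the current wording, and nothing says how the analysis would treat it.

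**Step 4. Follow-up duty.** Sections 11.3 and 11.4 end follow-up at resolution or at a judgement that the event is chronic or stable. Neither refers to the outcome code or to the end of treatment.

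**Step 5. Size.** Let *p* be the share of events truly resolved at a visit, and *q* the share of unresolved events that need no further treatment. If every such event were coded 'Recovered', the coded share would be *p* + (1 − *p*)*q*, an overstatement of (1 − *p*)*q*. The documents give neither input. With assumed values of *p* from 0.60 to 0.70 and *q* from 0.10 to 0.30, the overstatement runs from 0.30 × 0.10 = 0.03 to 0.40 × 0.30 = 0.12. This only shows how the formula behaves. It concerns the share coded 'Recovered', not time to resolution, and it is no estimate for this trial.

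**The case against.** The best defence is that the wording permits miscoding but does not compel it. A site that follows the lead-in would not call a persisting event recovered, and lasting effects have a code of their own. This stands in part: there is no evidence that any event was miscoded. But a site with an untreated event expected to clear has no other code that fits, so good intentions do not close the gap.

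A reader might go further and infer that the date treatment ends becomes the resolution date, so that time to resolution is wrong. The documents do not support this. No section derives the resolution date from the outcome code or from the end of treatment, and the form list in 11.2 shows no treatment end date.

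A reader might also infer that coding a related event 'Recovered' ends the duty to follow it. It does not. Under 11.3 and 11.4 that duty ends only at resolution or a chronic or stable judgement.

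Two further points limit the weight of the finding. Section 14.7 bases the safety assessment on incidence and seriousness, and no hypothesis test or alpha is attached to time to resolution. The document history says the outcome definitions were added in version 5.0 (October 2020), close to the end of recruitment in November 2020, so it is unclear which entries were coded under this wording.

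On the other side, the surgeon is blinded only until surgery (9.4) and the investigator completes the adverse-event forms (Table 1). Loose codes therefore leave room for coding that differs between arms. That is a possibility, and nothing in the documents shows that it occurred.

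**Conclusion.** The concern holds as a defect in the data definitions. 'Recovered' literally includes unresolved events that need no treatment, in conflict with the lead-in to the codes. 'Not Recovered, Ongoing' literally excludes untreated persisting events, which have no correct code unless they are judged unlikely ever to resolve. Outcome coding can therefore overstate recovery.

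Time to resolution is at risk for a separate reason: resolution is undefined, and the resolution-date field and the outcome code are not tied together. If sites enter a date because they have chosen 'Recovered', or if the analysis counts that code as resolved, durations would be too short and the share resolved too high. The documents do not show that either happens.

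The size cannot be computed, because the plan gives no event counts, no durations and no share of events left untreated. The conclusion rests on a literal reading of 11.2 and on the assumption that some events persist without treatment. The primary composite endpoint is unaffected. The correction is worth making because it is cheap and touches a named secondary endpoint.

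**What to change.** In 11.2 and the CRF guidelines:

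- Define 'Recovered' as 'the adverse event has resolved (signs and symptoms gone or back to baseline)', and delete the alternative that rests on treatment no longer being needed.
- Define 'Not Recovered, Ongoing' as 'the adverse event has not resolved, whether or not treatment or tests were prescribed'.

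In 14.6, state that time to resolution uses the recorded date of resolution, and that ongoing, chronic and lost-to-follow-up events are censored.

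For data already entered, use the existing EDC queries (17.2) only for events coded 'Recovered' that have no resolution date or carry an ongoing status. Both conditions can be read from fields on the form. A wider query keyed to the end of treatment would not be workable, since no such date is listed, and asking subjects to recall resolution dates long afterwards would add error.

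The cost is a small update to the CRF guidelines and one limited query round.

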11.3 Events Followed to Resolution

Any adverse event considered by the Investigator to be possibly, probably or definitely related to the Subchondroplasty procedure and/or AccuFill should be followed over the study period until resolution or until the Investigator determines the event is chronic or clinically stable.

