6.0 Study Objectives & Endpoints

6.1 Study Objectives

The primary objective of this study is to determine whether Subchondroplasty with arthroscopy is superior to arthroscopy alone for treatment of bone marrow lesions in the knee. Superiority will be evaluated in terms of composite clinical success (CCS) requiring freedom from subsequent secondary surgical intervention (SSSI) and among those free from SSSI, a clinically meaningful reduction in self-reported pain based on a validated measure of subject-reported pain. Conditional on showing superiority in terms of CCS, superiority in terms of improved ADL will then be tested as a conditional endpoint.

Secondary objectives include evaluation of other subject-reported outcomes measures; evaluating the safety profile by determining the incidence and time to resolution of post-operative complications and adverse events; comparing the incidence and time to subsequent secondary surgical intervention including re-operation and revision; and evaluating the use of healthcare resources and impact on productivity.

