10.6 Withdrawal and Study Re-Entry

Subjects may withdraw or be withdrawn at any time during the course of the study, per subject request or at the discretion of the investigator. Investigators may withdraw a subject due to non-compliance with the protocol or follow-up visit schedule, occurrence of adverse events, death, or other reasons per their professional opinion. The date and reason for subject withdrawal is to be documented on the **Study Exit Form**.

If a subject is withdrawn or terminated due to medical safety considerations because of an adverse event, the adverse event must be followed by medical attention until the investigator determines the event is chronic or clinically stable and all study data related to the event recorded.

When a subject withdraws or is withdrawn, all study procedures completed and data collected prior to the date of withdrawal will be submitted to the Sponsor and included in the study database, unless the subject requests otherwise in writing.

Should a subject who previously chose to withdraw or were considered lost-to-follow-up wish to re-enter the study, a new Informed Consent will be required. The site may resume scheduled follow-up visits according to their follow-up schedule.

Since the pre-determined sample size includes an additional 27 patients to account for lost-to follow-up, subjects that are withdrawn from the study will not be replaced.

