11.0 Safety Management—Medical Events/Adverse Events

Adverse events that occur either intraoperatively or during the follow-up phase of the study protocol are to be recorded on an Adverse Event Form whether noted by the Investigator or the subject. Sites should report only those adverse events that are related to the implant (AccuFill), Subchondroplasty Instrumentation (AccuPort Cannulas), or study procedure (Subchondroplasty and/or Arthroscopy), or those that are considered serious. Sites should also take into consideration the possibility of a temporal relationship between a potential adverse event and the study implant, instrumentation or procedure. Any events that are pre-existing (prior to surgery) are not considered adverse events, unless a pre-existing complication or event has changed in severity or intensity during the study period.

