11.4 Serious Adverse Events

If an AE is determined to be serious (i.e. an SAE), the Investigator(s) will determine the relationship of the adverse event to the procedure(s), device, or any commercial products used during the period of the study and complete an **Adverse Event Form**. Death is considered to be an outcome of an Adverse Event and documented on the Adverse Event Form. The actual cause of death (rather than the term “death”) should be recorded on the form. All SAEs will be followed until resolution or the Investigator judges the event to be chronic or stable.

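### Section 11.3 ties follow-up to resolution to Subchondroplasty and AccuFill, so non-serious arthroscopy-related events have no such rule and resolution dates may be less complete in the control arm

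*Combined protocol and SAP*

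**What the plan says.** The follow-up rule in Section 11.3 applies to events rated possibly, probably or definitely "related to the Subchondroplasty procedure and/or AccuFill should be followed over the study period until resolution", with chronic or stable status as the alternative end. Two other provisions require follow-up to an end state:

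- Section 11.4, whatever the relatedness: "All SAEs will be followed until resolution or the Investigator judges the event to be chronic or stable".
- Section 10.6, when a subject is withdrawn for medical safety reasons because of an event: "the adverse event must be followed by medical attention until the investigator determines the event is chronic or clinically stable".

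Reporting is wider than 11.3. Section 11.0 asks sites to report events related to the implant, the instrumentation "or study procedure (Subchondroplasty and/or Arthroscopy), or those that are considered serious". The adverse event form in Section 11.2 rates procedure relatedness in one combined field, "Relationship to Study Surgical Procedure (Subchondroplasty and/or Arthroscopy"), and has a field for "Status of Adverse Event or Date of Resolution" for each reported event.

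On use of the data, Section 6.1 has safety assessed by "determining the incidence and time to resolution of post-operative complications and adverse events". Item 6 of the secondary endpoints in Sections 6.3 and 14.6 reads "Incidence and time to resolution of post-operative complications and adverse events".

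**The concern.** A control subject who has not crossed over has had neither Subchondroplasty nor AccuFill, so none of that subject's events can meet the relatedness condition in 11.3. The protocol makes arthroscopy-related events reportable, then leaves them out of the rule that would secure their resolution dates. If dates are sought harder in one arm, a by-arm summary of time to resolution mixes how long events lasted with how long the site was told to look. Such a summary matters here because Section 7.0 gives adverse event monitoring as one reason for continuing follow-up after enrollment stopped.

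**Working it through.** No arithmetic applies: the documents give no event rates or resolution times. The check sets the sections side by side and asks, for each class of event, which rule requires follow-up to an end state.

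| Class of event | Arthroscopy alone, before cross-over | Subchondroplasty with arthroscopy |
|---|---|---|
| Serious | 11.4 | 11.4 |
| Led to reoperation or revision | recorded as serious (9.7.2), so 11.4 | same |
| Caused withdrawal for medical safety | 10.6 | 10.6 |
| Other non-serious, at least possibly related to Subchondroplasty or AccuFill | cannot arise | 11.3 |
| Other non-serious, related to arthroscopy only | no rule | no rule |

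**Step 1: the uncovered class.** The last row is the gap. Under 11.0 a non-serious event is reportable only if it is related to the implant, the instrumentation or a study procedure. Before cross-over, arthroscopy is the only one of these that a control subject has had. The last row therefore holds every reportable non-serious control event not caught by rows two and three. After cross-over, a control subject's later events can fall under 11.3.

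**Step 2: why the gap falls unevenly.** The last row exists in both arms, but similar events can land in different rows. Both procedures are done on the same knee in one operation (9.5.2). Sections 5.7.2 and 5.7.3 both list infection, hematoma and nerve or vascular injury as risks. Under 11.2 an event may be rated possibly related even when another cause is present. A non-serious hematoma in the Subchondroplasty arm can thus readily fall under 11.3, while the same hematoma in a control subject cannot. The surgeon knows the allocation from the time of surgery (9.4), so relatedness can be rated with the arm known.

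**Step 3: whether another provision fills the gap.**

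- The form field accepts a status in place of a date, and 11.2 allows an outcome of not recovered and ongoing.
- The calls (9.7, 9.7.2) ask about events that occurred since the previous contact. Neither section asks for an update on events still open.
- Completeness checks (10.2.1, 15.0) and lock (17.3) require complete forms and no outstanding queries. A form showing an ongoing event can satisfy both.

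A site can therefore follow every written rule and still leave a non-serious control-arm event without a resolution date.

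**Step 4: what the analysis plan does with these dates.** Section 14.7 plans counts, percentages, event counts by interval, and listings that include onset and resolution status. The Synopsis tabulates adverse events by group. No method for time to resolution is given, and no rule for events still unresolved. If open events are counted as unresolved, the arm followed less closely looks slower to resolve. If only dated events are summarized, that arm may look faster, because its late resolutions are missing. The direction cannot be stated in advance.

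**The case against.** The best case against the point is that resolution data are collected in both arms. The status or date field exists for every reported event, both arms have the same seven calls to 24 months, and missing or unclear entries are queried. Section 11.3 sets a minimum and does not stop a site from recording resolution of other events. This stands as a reason why the difference may be small. It does not remove the gap, since none of these provisions requires an open event to be revisited.

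Three stronger readings are tempting, and the documents do not support them:

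- *That no non-serious control-arm event need ever be followed.* Section 10.6 covers events that cause withdrawal for medical safety in either arm, 9.7.2 makes events leading to reoperation serious, and crossed-over subjects can come under 11.3.
- *That the split is purely by arm.* The rule turns on relatedness, and Subchondroplasty-arm events attributed to arthroscopy alone are outside it too.
- *That a planned comparison is invalid and the safety objective goes unanswered.* For time to resolution, 6.1 speaks of determining and not of comparing, endpoint 6 is not worded as a comparison, and 14.7 contains no between-arm test. Incidence, seriousness, severity and relatedness do not depend on 11.3.

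It is also fair to say that recruitment ended in November 2020, so many perioperative events had already been handled under the existing rule. That limits what a change can recover but does not make it pointless.

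**Conclusion.** The point holds as an inconsistency in scope between 11.3 and Sections 11.0 and 11.2, with a possible effect on one secondary safety endpoint. Resolution dates may be less complete in the control arm, and a by-arm summary of time to resolution may be biased. Neither direction nor size can be derived from the documents. The conclusion assumes that some sites do no more than the text requires, and that endpoint 6 will be shown or read by arm. The primary endpoint is not touched. The change is worth making because it is cheap, but this is not a reason to doubt the safety data as a whole.

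**What to change.** 1. In 11.3, widen the relatedness condition to either study procedure (Subchondroplasty or arthroscopy), AccuFill and the Subchondroplasty instrumentation. This is the scope of 11.0 and 11.2, and it gives one rule for both arms that also takes in arthroscopy-only events in the Subchondroplasty arm.
2. At each remaining call, have the coordinator ask for the current status or resolution date of every open adverse event.
3. Before lock, query all open adverse events in both arms. Querying control subjects alone would create a new imbalance, because arthroscopy-only events in the other arm have been equally outside the rule. This step remains available if the calls have finished.
4. In 14.7, state how unresolved events enter any summary of time to resolution.

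The cost is a small protocol amendment, with sponsor approval and IRB or REB approval where required (13.2), at up to 25 sites, and slightly more site work on calls and queries. No visit or assessor is added.
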